1.6 GLP Toxicology

GLP 28-day repeat dose toxicology studies were performed in both rats and dogs at doses of 10, 30, and 100 mg/kg/day of BBI608 by oral gavage.

In the rat study, 100 mg/kg was not tolerated by the male rats. Toxic observations include significant weight loss, soft feces and diarrhea, and decreased food consumption, which led to early sacrifice. These symptoms recovered in the remaining male rats within 14 days after termination of dosing. Female rats receiving 100 mg/kg/day showed weight loss during the first week of dosing; however, weight recovered during the continued dosing phase without significant abnormal clinical observations.

In the rat study, abnormal laboratory findings (azotemia, hyponatremia, hypochloremia, hyperkalemia, polycythemia, neutrophilia, monocytosis, and lymphopenia) were observed primarily in moribund male rats dosed at 100 mg/kg. These findings are consistent with acute renal failure in the setting of dehydration and diarrhea. In rats dosed at 100 mg/kg for 28 days, there was a mild decrease in sodium, chloride, and albumin levels and mild elevation of white blood cells, red blood cells, neutrophils, lymphocytes and monocytes. No significant abnormal laboratory findings were seen in recovered rats, suggesting that these abnormal laboratory findings are reversible. There were no abnormal laboratory findings in rats dosed at 10 and 30 mg/kg.

In the rat study, histopathological findings were noted in the rats dosed at 100 mg/kg, primarily in moribund male rats, including microscopic changes in the stomach and urinary bladder (focal or multifocal chronic ulceration, epithelial hyperplasia, chronic active

inflammation or hemorrhagic changes), in lymphoid tissues (mild to marked lymphoid atrophy with mild to moderate lymphocyte apoptosis in thymus, mild to moderate lymphoid atrophy and mild to moderate mastocytosis in mesenteric lymph nodes, mild to moderate lymphoid atrophy in two moribund male rats dosed at 100 mg/kg, and some elevation of hemosiderosis in the spleen) and in adrenal glands (mild cortical vacuolation). These findings were considered to be non-specific changes related to the test vehicle in the setting of dehydration and diarrhea. There were no significant histopathological findings in recovered rats, suggesting that these histopathological changes are reversible. There was no significant test vehicle related microscopic changes in rats dosed at 30 mg/kg and at 10 mg/kg.

In the rat study, toxicokinetics showed that all dose groups in rats achieved BBI608 exposure at a level well above the predicted exposure levels needed for efficacy, and exposure lasted beyond 10 hours.

In the dog study, toxicity was observed in dogs receiving 100 mg/kg/day. Toxic symptoms consisted of mild weight loss, emesis, diarrhea, and mucoid and soft feces. These adverse effects were reversible within 14 days in the setting of continued dosing. No treatment-related clinical pathological, gross pathological, or histopathological effects were observed at any dose level. All dose groups achieved plasma levels of BBI608 above the predicted levels needed for efficacy, and exposure lasted beyond 10 hours.

The *no observable adverse effect level* (NOAEL, based on clinical observation, laboratory tests, gross and histopathological changes) for rats administered BBI608 daily orally over 28 days was 30 mg/kg/day (human equivalent dose: 180 mg/m²) and the NOAEL in dogs administered BBI608 daily orally over 28 days was 30 mg/kg/day (human equivalent dose: 600 mg/m²).

1.7 Safety and Encouraging Signs of Antitumor Activity in Phase I and II Studies

In the Phase I dose escalation study of BBI608 monotherapy, 14 cohorts (N=41) were dosed from 20 mg to 2000 mg/day. All of the patients in this study were in the last line of treatment setting. Eighteen (44%) of the patients had CRC, which was the most common type of cancer studied in this trial. Other types of cancers varied from 2-7% of the total, and included gastric/GEJ, pancreatic, NSCLC, prostate, head and neck, melanoma and others. The vast majority of the patients (78%) in this study had progressed on ≥ 3 prior regimens. Adverse events were generally mild, including grade 1-2 diarrhea, nausea, anorexia and fatigue with a total of 4 grade 3 events (diarrhea and fatigue). MTD was not reached. At 400 mg/day, the plasma concentration of BBI608 was sustained at a concentration > 1.5 uM (several fold above the IC₅₀ [avg.~0.09 uM]) for > 8 hours. RP2D has been determined to be 480 mg bid. Among those evaluable for tumor response (using RECIST 1.1 criteria), disease control (disease stabilization and regression) was observed in 65% of patients. Prolonged time to progression was observed in 46% of evaluable patients, including patients with CRC, head & neck, gastric, ovarian, melanoma, and breast cancers. In the subset of patients with CRC (N=18), disease control was seen in 67% of those evaluable. Median progression free survival (PFS) and overall survival (OS) of 14 and 47 weeks, respectively, were observed in evaluable CRC patients. Median OS for biomarker-positive (nuclear β -catenin and high p-STAT3) CRC patients was 53 weeks and 54 weeks, respectively. In this study, BBI608 has shown a favorable safety and PK profile, and encouraging signs of activity, particularly in CRC.

In addition, BBI608 has been evaluated in combination therapy in the Phase Ib/II studies. BBI608 has been safely combined at full dose with paclitaxel or capecitabine (BBI608-201 and BBI608-224, respectively), with a similar adverse event profile compared to that of either BBI608 or paclitaxel monotherapy. The RP2D of BBI608 in combination with weekly paclitaxel or capecitabine has been determined to be 480 mg twice daily.

In a previously conducted subcohort of BBI608-201 with Budesonide prophylaxis for GI symptoms, budesonide an oral topical corticosteroid led to marked decrease in the incidence and severity of gastrointestinal symptoms. Budesonide decreased the incidence and severity of diarrhea, abdominal pain, nausea, vomiting and fatigue in patients who received oral Budesonide 9mg po QD when combined with BBI608 at 480mg either as monotherapy or combined with weekly Paclitaxel and at 240mg either as monotherapy or combined with weekly Paclitaxel. Plasma levels of BBI608 in subjects taking budesonide were similar to the ones that had not received budesonide prophylaxis at BBI608 doses of 240mg and 480mg bid, either with or without the addition of weekly Paclitaxel infusion.

Given the clinical data thus far, and the encouraging *in vitro* and *in vivo* results seen with the combination of BBI608 with TMZ, further evaluation of BBI608 in combination therapy to treat GBM is warranted.

2 STUDY OBJECTIVES

2.1 Primary Objectives

The primary objective of this study for the Phase Ib component is:

- To determine the safety, tolerability of BBI608 when administered in combination with temozolomide (TMZ).

The primary endpoint of this study for the Phase II component is:

- To determine progression-free survival at 6-months (PFS-6).

2.2 Secondary Objectives

The secondary objectives for the Phase Ib component of this study are:

- To assess preliminary anti-cancer activity of BBI608 when administered in combination with TMZ.
- To determine the pharmacokinetic profile of BBI608 when administered in combination with TMZ.
- To determine the pharmacodynamics (i.e., identify biomarkers) of BBI608 when administered as monotherapy prior to repeat surgical resection and when administered in combination with TMZ.

The secondary endpoints of this study for the Phase II component are:

- To assess the median progression free survival (PFS).

- To assess the median overall survival (OS).
- To assess the disease control rate (DCR).
- To assess the objective response rate (ORR), when applicable.

3 SELECTION OF STUDY POPULATION

This study will be conducted in patients with histologically confirmed GBM at first recurrence of disease following front-line therapy that includes maximal resection, radiotherapy, and chemotherapy with TMZ (the latter is allowed but not mandatory for enrollment), and for whom treatment with TMZ is an appropriate treatment option in the judgment of physician investigators and who may or may not be eligible for repeat surgical resection. Patients who are eligible for further surgical resection will be enrolled into Arm A. Patients who are not eligible for further resection will be enrolled into Arm B.

3.1 Inclusion Criteria

Each patient must meet the following criteria to be enrolled in this study.

1. Signed written informed consent must be obtained and documented according to International Conference on Harmonisation (ICH) and local regulatory requirements
2. A histologically confirmed supratentorial GBM at first recurrence/progression following standard front-line therapy, for which treatment with TMZ would be acceptable as determined by the Investigator.
 - a. Recurrence is defined as progression following initial therapy (i.e. radiation+/- chemo, if that was used as initial therapy). The intent therefore is that the patient has had no more than 1 prior treatment regimen.
3. Previously received standard front-line GBM treatment including maximal surgical resection followed by external beam radiation therapy.
 - a. Prior concurrent chemoradiation with TMZ is allowed but not mandatory. A minimum of 12 weeks following the last dose of Radiotherapy or TMZ-Radiotherapy must occur prior to the first documented progression. After that period in patients receiving adjuvant TMZ a wash out period of 4 weeks before first dose of BBI608 is required.
4. Patients may or may not be candidates for repeat surgical resection of the recurrent/progressed GBM.
5. Patients must have unequivocal evidence of tumor recurrence/progression by MRI at a minimum of 12 weeks following completion of chemoradiation or radiation therapy.
6. Baseline scan performed within 28 days of enrollment.
7. Patients on concurrent corticosteroid treatment are eligible for enrollment as long as they are on a stable or decreasing dose of corticosteroids (or no corticosteroids) and neurologically stable from the time of their baseline scan and/or at least 5 days before starting treatment with BBI608. During this period the maximum total daily dose of dexamethasone should not exceed 8 mg administered orally (or bioequivalent).

8. Patients must have measurable or non-measurable disease by RANO criteria.
9. Patients treated with CYP1A2 enzyme inducing anti-epileptics (including phenobarbital, phenytoin, and carbamazepine) must be switched to an alternative anti-epileptic agent at least 14 days prior to first dose of BBI608.
10. ≥ 18 years of age.
11. ECOG (Eastern Oncology Cooperative Group) performance status of 0 or 1 (corresponding to a Karnofsky performance status score $\geq 70\%$) (Appendix C).
12. Male or female patients of child-producing potential agree to use contraception or to avoid contributing to a pregnancy or becoming pregnant, respectively, during the study and for 30 days after the last BBI608 dose.
13. Females of childbearing potential have a negative serum pregnancy test.
14. Aspartate transaminase (AST) and alanine transaminase (ALT) levels ≤ 3.0 x upper limit of normal (ULN).
15. Hemoglobin (Hgb) ≥ 9 g/dl.
16. Total bilirubin level $\leq 1.5 \times$ ULN.
17. Creatinine level $\leq 1.5 \times$ ULN or creatinine clearance > 60 mL/min/1.73 m² for patients with creatinine levels above institutional normal (as determined by Cockcroft-Gault equation).
18. Absolute neutrophil count $\geq 1.5 \times 10^9$ /L.
19. Platelets $\geq 100 \times 10^9$ /L.
20. Life expectancy estimated at ≥ 3 months.
21. Patients have recovered from toxicities (to Grade ≤ 1) related to their previous therapy.

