5.4.2 Surgical Resection of Recurrent GBM

ONLY patients enrolled into Arm A will undergo surgical resection of GBM.

BBI608 will be administered for 7 (\pm 2) days prior to a planned surgical resection of recurrent GBM. BBI608 will be administered on the morning of the surgical procedure (Run-in Week 2 Day 8) and BBI608 will remain held pending clinical post-operative recovery of the patient as determined by the investigator, for up to 28 days after surgery. Tumor sample will be obtained at time of surgical resection from T1/gadolinium enhanced lesion(s) as well as T2/FLAIR infiltrating tumor lesions and will be used to investigate BBI608 presence in the resected tumor tissue and will be used for pharmacodynamics analysis (please see the Laboratory Manual for additional information). Additionally, blood sample will be obtained at time of surgery to evaluate BBI608 pharmacokinetic (PK) exposure in the plasma (please see the Laboratory Manual for additional information). The time of BBI608 administration on the day of surgery and the collection times of blood sample will be recorded.

Tumor samples that are obtained at the time of surgical resection and are labeled with study protocol identification number and patient identification number will be sent to a regulatory authority-approved tumor bank affiliated with the study site, or to the study site pathology department if the site does not have a regulatory authority-approved tumor bank. In the event

that there is difficulty with establishment of histological diagnosis, tumor tissue will be made available to the pathology department at all study sites. Processing of all tumor tissue will include creation of both fresh frozen samples for PK analysis as well as blocks of formalin fixed paraffin-embedded (FFPE) samples for PD analysis.

An MRI will be performed 48-72 hours following surgery and will be used as the baseline scan for the purposes of tumor response evaluation in the patients who undergo surgical resection.

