9.3 Response Criteria

Radiographic response should be determined in comparison to the tumor measurement obtained at pretreatment baseline for determination of response, and the smallest tumor measurement at either pretreatment baseline or after initiation of therapy for determination of progression. For patients in Arm A who undergo surgical resection, the post-operative baseline scan (performed 48-72 hours after surgery) should be used for response assessment.

Response criteria are outlined below. In the event that the radiographic changes are equivocal and it is unclear whether the patient is stable or has developed progressive disease, it is permissible to continue treatment and observe the patient closely, for example at 4-week intervals. If subsequent imaging studies demonstrate that progression has occurred, the date of progression should be the date of the scan at which progression was first suspected.

Complete Response*

Requires ALL of the following:

1. Complete disappearance of all enhancing measurable and non-measurable disease sustained for at least 4 weeks.
2. No new lesions.
3. Stable or improved non-enhancing (T2/FLAIR) lesions.
4. Patients must be off corticosteroids (or on physiologic replacement doses only).
5. Patients must be stable or improved clinically.[#]

Partial Response*

Requires ALL of the following:

1. Greater than or equal to 50% decrease compared to baseline in the sum of products of perpendicular diameters of all measurable enhancing lesions sustained for at least 4 weeks.
2. No progression of non-measurable disease.
3. No new lesions.
4. Stable or improved non-enhancing (T2/FLAIR) lesions on same or lower dose of corticosteroids compared to baseline scan.
5. The corticosteroid dose at the time of the scan evaluation should be no greater than the dose at time of baseline scan.
6. Patients must be stable or improved clinically.#

Stable Disease

Requires ALL of the following:

1. Does not qualify for complete response, partial response, or progression.

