2. Stable non-enhancing (T2/FLAIR) lesions on same or lower dose of corticosteroids compared to baseline scan. IN the event that the corticosteroid dose was increased for new symptoms and signs without confirmation of disease progression on neuroimaging, and subsequent follow-up imaging shows that this increase in corticosteroids was required because of disease progression, the last scan considered to show stable disease will be the scan obtained when the corticosteroid use was equivalent to the baseline dose.
3. Patients must be stable clinically.#

Progressive Disease

Defined by ANY of the following:

1. Greater than 25% increase in the sum of the products of perpendicular diameters of enhancing lesions compared to the smallest tumor measurement obtained either at baseline (if no decrease) or best response, on stable or increasing doses of corticosteroids.**
2. Significant increase in T2/FLAIR non-enhancing lesion on stable or increasing doses of corticosteroids compared to baseline scan or best response following initiation of therapy,* not due to co-morbid events (e.g. radiation therapy, demyelination, ischemic injury, infection, seizures, post-operative changes, or other treatment effects).
3. Any new lesion.
4. Clear clinical deterioration not attributable to other causes apart from the tumor (e.g. seizures, medication side effects, complications of therapy, cerebrovascular events, infection, etc.) or changes in corticosteroid dose.#
5. Failure to return for evaluation due to death or deteriorating condition.
6. Unequivocal progression of non-measurable disease.

*Patients with non-measurable disease only cannot have a complete or partial response. The best response possible is stable disease.

**Stable doses of corticosteroids include patients not on corticosteroids.

#Clinical status will be assessed via ECOG Performance Score.

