9.4 Evaluation of Best Overall Response

The best overall response is the best response recorded from the start of the treatment until disease progression/recurrence and is determined as indicated in the table below:

The table below provides the summary of the RANO response criteria.

Criterion	Complete Response	Partial Response	Stable Disease	Progressive Disease
T1/Gd enhanced lesions	None	≥50% decrease	≤50% decrease to <25% increase	≥25% increase*
T2/FLAIR	Stable or decreasing	Stable or decreasing	Stable or decreasing	Increasing*
New Lesion	None	None	None	Present*
Corticosteroids	None	Stable or decreasing	Stable or decreasing	NA**
Clinical Status#	Stable or improving	Stable or improving	Stable or improving	Worsening*
Requirement for Response	ALL	ALL	ALL	Any*

*Progressive Disease occurs when any of the criteria marked by * are present.

**Increase in corticosteroid dose in isolation of other criteria will not be taken into account in the assessment of progressive disease in the absence of persistent clinical status deterioration.

#Clinical status will be assessed via ECOG Performance Score

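### For a patient with no enhancing tumour on the response baseline scan, the summary table and the full response criteria give different answers, and either one distorts ORR

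*Protocol*

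**What the plan says.** **Entry.** Protocol 3.1, item 8: "Patients must have measurable or non-measurable disease by RANO criteria". No later section asks for disease on the post-operative scan.

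**Response baseline in Arm A.** Protocol 5.4.2 says the post-operative MRI "will be used as the baseline scan for the purposes of tumor response evaluation in the patients who undergo surgical resection". Protocol 9.3 agrees: "For patients in Arm A who undergo surgical resection, the post-operative baseline scan (performed 48-72 hours after surgery) should be used for response assessment". SAP 7.2 repeats the rule.

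**Full criteria.** Protocol 9.3 gives the general principle: "Radiographic response should be determined in comparison to the tumor measurement obtained at pretreatment baseline for determination of response". Its first CR item is "Complete disappearance of all enhancing measurable and non-measurable disease sustained for at least 4 weeks". CR also needs clinical stability and no corticosteroids beyond physiologic replacement. A footnote caps one group at SD: "Patients with non-measurable disease only cannot have a complete or partial response". SAP Table 2 carries the same items and footnote.

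**Summary table.** Protocol 9.4 says best overall response runs "until disease progression/recurrence and is determined as indicated in the table below". In that table the CR entry for T1/Gd enhanced lesions is simply *None*, with no reference to baseline. The Overall Response table in SAP 10.1 has the same entry.

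**Counting.** SAP 10.1 confirms CR from two CR statuses at least four weeks apart. SAP 8.2.3.1 bases the primary ORR estimate on the full analysis set, which is everyone given at least one dose (SAP 6.1). SAP 7.1 treats a missing baseline tumour evaluation as a non-response. It has no rule for a baseline scan that was done and shows nothing.

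**The concern.** After a complete resection the response baseline may contain nothing to measure. No rule in either document names that patient, and the rules that come closest disagree. One makes the patient a complete responder for not having recurred. The other makes response impossible but still counts the patient in the denominator.

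ORR and best overall response are reported by arm in a study with no hypothesis test, so the descriptive figures carry the message about activity. A complete response in recurrent glioblastoma would be read as drug effect. If sites or programmers apply different rules, Arm A ORR becomes a mixture with no clear meaning, and comparing it with Arm B becomes harder still.

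**Working it through.** **The plan's own figure.** The documents state no figure for ORR. Their only sizing figure is for PFS-6: at 20% with n = 30 (6/30), the exact two-sided 80% interval has a lower bound above 10%. Clopper-Pearson gives 10.9% to 32.5%, so the statement reproduces. It does not bear on this point.

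**The rules applied to one patient.** Take a patient with no enhancing disease at the post-operative baseline, no recurrence, stable clinical status and no steroids.

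- *Summary table:* no enhancing lesion, T2/FLAIR stable, no new lesion, no steroids, clinically stable. Every CR row is met, and a second such scan four or more weeks later confirms it.
- *Full criteria:* response is judged against baseline, and nothing present at baseline can disappear. No CR or PR.
- *SD cap:* it applies to non-measurable disease only. Under Protocol 9, a cavity rim without a nodule of at least 10 mm is non-measurable, so that patient is capped. A patient with no disease is not named.
- *Denominator:* the full analysis set keeps the patient either way. The per-protocol set in Protocol 10.1 is defined by exposure and would not remove the patient for this reason either.

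**Effect on ORR.** Inputs: n = 30 (Protocol 3.3); k = patients with no residual enhancement (assumed); c = share of those k who meet the other CR rows and are confirmed (assumed); r = true response rate in the remaining, measurable patients (assumed).

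- Table reading: [k × c + (30 - k) × r] / 30
- Full-criteria reading: (30 - k) × r / 30
- Measurable patients only: r

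With no true response (r = 0) and c = 1, with exact 95% intervals:

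| k | Table reading | Full criteria | Measurable only |
|---|---|---|---|
| 3 | 3/30 = 10% (2.1-26.5%) | 0/30 (0-11.6%) | 0/27 (0-12.8%) |
| 6 | 6/30 = 20% (7.7-38.6%) | 0/30 (0-11.6%) | 0/24 (0-14.2%) |
| 9 | 9/30 = 30% (14.7-49.4%) | 0/30 (0-11.6%) | 0/21 (0-16.1%) |

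With r = 10% and k = 9:

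- Table, c = 1: (9 + 2.1)/30 = 37%
- Table, c = 0.5: (4.5 + 2.1)/30 = 22%
- Full criteria: 2.1/30 = 7%
- Measurable only: 2.1/21 = 10%

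**How far below k/30 the table reading might fall.** Not all k patients stay progression-free long enough to be confirmed. As an illustration, assume 30-50% of Arm A have no residual enhancement and 50-75% of those still unprogressed are steroid-free and stable. Assume exponential PFS with a 6-month rate of 10-20%. The shortest nominal path to the week-16 scan is 5 + 15 + 112 = 132 days, or 4.34 months.

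- Unprogressed: 0.10^(4.34/6) = 0.19 to 0.20^(4.34/6) = 0.31
- Low end: 0.30 × 0.19 × 0.50 = 2.8%, or 0.9 of 30
- High end: 0.50 × 0.31 × 0.75 = 11.6%, or 3.5 of 30

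Earlier confirmation, for example at the roughly four-week confirmatory scan in SAP 10.1, would raise this. A longer run-in or recovery would lower it.

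**The case against.** The strongest reply is that the table is labelled a summary, and that the criteria it summarises settle the case: disease must disappear relative to the post-operative baseline, and nothing can disappear from an empty cavity. The SAP does not repeat the sentence making the table the determining instrument. It derives best response from objective statuses, and ORR rests on investigator assessment. An investigator applying RANO with care would not call this patient a complete responder.

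Much of that stands. A reader might infer that Arm A ORR simply counts surgery, or that the footnote is the only safeguard. The documents do not support either inference. The full CR criterion is a second safeguard, and under it the bias in ORR runs downward.

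A reader might also infer that Arm B is immune. It is not clearly so: Protocol 3.2, item 6a and Protocol 4.1 admit Arm B patients who had a repeat resection before entry. Nor is inclusion item 8 itself an error.

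The reply does not remove the conflict. Protocol 9.4 calls the table a summary and also says best response is determined from it. The PR item names baseline as comparator; the CR item does not. Best response is counted from the start of treatment, which in Arm A precedes surgery, when tumour was present. Two careful sites could score the same patient differently. The protocol qualifies ORR with an undefined proviso about applicability, which does not decide the case. Accepting the reply in full still leaves the diluted denominator.

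**Conclusion.** The point holds as a conflict between rules, with the direction of bias depending on which rule is applied. Relative to the full criteria, the table reading can add up to k/30 to ORR: 10, 20 or 30 percentage points for k = 3, 6 or 9. The full criteria multiply the measurable-patient rate by (30 - k)/30, for example 10% to 7% at k = 9.

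The documents give neither k nor the share of such patients who would be steroid-free, stable and confirmed, so these figures are illustrations. They take 30 patients in the arm; the table maxima also assume that every such patient meets the other CR rows and is confirmed. Arm A also allows biopsy and patients who are never resected, which limits k.

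The consequence is confined to ORR, best overall response and, if these patients are labelled SD, DCR. PFS-6 does not depend directly on the CR or SD label. This should be corrected, but it does not threaten the primary endpoint.

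**What to change.** In Protocol 9.3 and 9.4, SAP 8.2.3.1, and SAP Table 2 and the Overall Response table:

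1. State that CR or PR requires measurable enhancing disease on the response baseline scan, in either arm.
2. Align the CR entry for enhancing lesions in both summary tables with that rule.
3. Name the category for patients with no disease on that scan, for example not evaluable for response but still followed for PFS and OS, and state how they count in DCR. A cap at SD alone would not be enough: it would credit them to DCR and leave the ORR denominator diluted.
4. Report ORR among patients with measurable disease at the response baseline, alongside the full analysis set figure.
5. Report, by arm, how many patients had no residual enhancement at that scan.

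For Arm B patients resected before entry, the plan should also say whether the baseline scan must follow the operation; Protocol 5.3 does not.

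The cost is a few sentences and one table entry in each document. The post-operative MRI is already scheduled, so no new data are needed. The measurable-disease ORR will have a smaller denominator and a wider interval (with no responders, an upper bound of 16.1% for 0/21 against 11.6% for 0/30), and the reported Arm A ORR may be lower.
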